10.8 Toxicity

All adverse events, including laboratory abnormalities, will be collected, recorded, and graded according to the National Cancer Institute (NCI) CTCAE, version 5.0.

10.9 Compliance

Patient's medication compliance will be evaluated by using medication logs/diaries where patient will document when and how often they use either medication each day (Appendix 5). They will bring in medication log/diary at every clinic visit.

10.10 Table 4. Overview of time points for sampling and clinical assessment

	Baseline	Cycle 1 Day 1 (Within 14 days of baseline)	Cycle 1 Day 8 (+/-7 days)	Cycle 1 Day 15 (+/-7 days)	4 weeks/ End of Cycle 1 (+/- 14 days)	12 weeks / End of Cycle 3 (+/- 21 days)
MD/RN assessment	Visit		Visit or telephone assessment	Visit or telephone assessment	Visit or telephone assessment	Visit
Stool studies GI pathogens ^a	Xa					
Triglycerides	X					
CBC	X					X
Comp	X					X
SPEP, IFE and FLC	X					X
Stool Diary (response assessment) and Bristol Stool Scale ^b	Х		X	х	Х	Х
PRO-CTCAE	X		X	Х	Х	Х
Nutritional Survey ^c						Х
PK studies ^d		Χq	Xq			
Research stool samples ^e	Х					X

- a. Stool studies for GI pathogens should be collected prior to starting colesevelam but do not need to be resulted prior to starting Day 1 dose of colesevelam, unless infection is suspsected by the treating investigator.
- b. Response assessments (Stool diaries) will be done at Cycle 1 Day 8, Cycle 1 Day 15, end of Cycle 1 (week 4) and end of Cycle 3 (week 12). If diarrhea does not improve by at least 1 grade from baseline (using CTCAE version 5.0) or to patient's baseline bowel pattern by the end of Cycle 1 they will be removed from study.
- c. Patients will complete one nutrtional survey ("Food and Activitity Questionaire" survey will be used) and return at week 12 visit.

- d. Lenalidomide pharmacokinetics will be assessed in up to 15 patients to assess possible drug interactions between lenalidomide and colesevelam. In these patients, a blood sample will be drawn pre- and 2 hours post the first colesevelam dose (day 1), as well as pre- and 2 hours post colesevelam on day 8 after initiation of colesevelam.
- e. Research stool samples will be collected at baseline and after 12 weeks of treatment for microbiota and bile acid studies.

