8.0 PRETREATMENT EVALUATION

Evaluation of Inclusion and Exclusion criteria

The pretreatment evaluation can be done either during screening or up to 14 days before start of treatment on study or at baseline. In the event that the samples (stool studies to exclude GI pathogens and serum triglycerides) are taken at baseline, the patient can start study drug and will be taken off study if failure to fulfill inclusion criteria.

Grading of diarrhea as an adverse event is graded according to CTCAE version 5.0. To be eligible on the study, patients need to have grade 1 or more diarrhea according to the CTCAE definition. The CTCAE definition can be found at the National Institutes of Health website. https://ctep.cancer.gov/protocolDevelopment/electronic applications/ctc.htm

Table 2. Diarrhea grading according to CTCAE version 5.0

Grade	Description			
Grade 0	No diarrhea present			
Grade 1	Increase of <4 stools per day over baseline, mild increase in ostomy output compared to baseline			
Grade 2	Increase of 4-6 stools per day over baseline, moderate increase in ostomy output compared to baseline; limiting instrumental ADL			
Grade 3	Increase of ≥7 stools per day over baseline; hospitalization indicated; severe increase in ostomy output compared to baseline; limiting self care ADL			
Grade 4	Life-threatening consequences; urgent intervention indicated			

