8.4 Diarrhea assessments

Diarrhea assessments using the CTCAE scale will be performed at screening (within 7 days before dosing on Cycle 1 Day 1). Diarrhea will be assessed using the CTCAE grading for the primary endpoint. Frequency and consistency of bowel movements will be recorded using a diarrhea questionnaire (Appendix 2). The Bristol Stool Form Scale will be used to evaluate diarrhea and stool consistency (Appendix 3).

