9.1 Treatment regimen

Only patients with grade 1 or more (CTCAE grading) diarrhea while on lenalidomide maintenance can initiate treatment with colesevelam on the study.

The treatment arm will be:

- The starting dose of colesevelam is 1250 mg (625 mg x 2) with food once daily and dose can be increased (6 tablets max per day) based on tolerability and efficacy
- Colesevelam should be spaced out from lenalidomide and other interacting medications by at least 4 hours

- Colesevelam is given continuously and patients will be treated for up to 12 weeks on study
- Treatment will continue until drug-related toxicity, worsening diarrhea, or unimproved diarrhea at 2 weeks despite increased dosage of the study drug or for a maximum of 12 weeks of treatment
- Patients who respond can continue on colesevelam after the 12 weeks of study treatment. Coverage for colesevelam costs after the 12 weeks will not be covered by the trial but will go through patient's insurance.

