10.4 Diarrhea assessments (primary endpoint)

Diarrhea assessments using the CTCAE scale will be performed at baseline (day 1 of colesevelam), at 1 week (+/- 2 days), 2 weeks (+/- 2 days), 4 weeks (+/- 7 days), and at 12

weeks (+/- 7 days). The assessment on week 1, 2, and 4 can be carried out as a telephone call by the treating physician or research nurse for reasons of convenience. In this event, the information regarding response will be collected over the phone and questionnaires will be handed in or sent to MSK.

Frequency and consistency of diarrhea/bowel movements will be recorded using a diarrhea questionnaire (Appendix 2). This will be used to grade the diarrhea according to the CTCAE scale (CTCAE, see section 8.0, page 15).¹⁴

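### Table 4 takes the pre-treatment diarrhea grade up to 14 days before the first dose and schedules none on Day 1, whereas Section 10.4 sets baseline on Day 1, so a pre-dose change can be counted as response.

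*Combined protocol and SAP*

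**What the plan says.** Several places date the pre-treatment assessment:

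- Section 10.4, the primary-endpoint section, states: "Diarrhea assessments using the CTCAE scale will be performed at baseline (day 1 of colesevelam)". Section 10.5 gives the same day for GI symptoms by PRO-CTCAE. It gives no baseline day for the Bristol scale.
- Section 8.4, under pretreatment evaluation, has a CTCAE grading "performed at screening (within 7 days before dosing on Cycle 1 Day 1)".
- Section 8.0 lets the pretreatment evaluation take place during screening, or "up to 14 days before start of treatment on study or at baseline".
- Table 4 has a Baseline column and a separate column headed "Cycle 1 Day 1 (Within 14 days of baseline)". The row for stool diary (response assessment) and Bristol scale, the PRO-CTCAE row and the MD/RN assessment row are all marked at Baseline and empty on Day 1. Only the PK row is marked on Day 1.
- Footnote b to Table 4 says: "Response assessments (Stool diaries) will be done at Cycle 1 Day 8, Cycle 1 Day 15, end of Cycle 1 (week 4)" and at week 12. It lists no Day 1 grading and judges improvement against baseline.

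Section 9.1 adds a condition for starting: "Only patients with grade 1 or more (CTCAE grading) diarrhea while on lenalidomide maintenance can initiate treatment with colesevelam on the study".

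**The concern.** The primary endpoint is a change in grade, so the date of the reference grade is part of its definition. Section 10.4 and Table 4 give different dates, and staff are likely to work from the table.

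Under Table 4, a patient graded 2 at Baseline who has drifted to grade 1 by Day 1 already meets the 1-grade definition of response in Sections 4.1 and 12.0 without having taken a tablet. A patient who has settled to grade 0 should not start under Section 9.1, but Table 4 schedules neither a grading nor a clinical contact on Day 1 at which to notice.

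Four features of the plan make such drift matter:

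- Patients are approached when they report diarrhea (Section 7.0), so the first grade tends to be high.
- Each grade rests on recall of two days (Section 12.0).
- A single good assessment within four weeks is enough (Section 14.0).
- There is no control arm in which the same drift would show.

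The Bristol and PRO-CTCAE changes have the same weakness. The error can also run the other way: a patient who worsens before Day 1 can be scored as worsening on drug.

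**Working it through.** **1. Timing, side by side**

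| Source | Pre-treatment diarrhea assessment | Gap to first dose |
|---|---|---|
| Section 10.4 | Baseline grade, day 1 of colesevelam | 0 days |
| Section 8.4 | Screening grade | up to 7 days |
| Table 4 | Baseline column, nothing on Day 1 | up to 14 days |

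The first two rows can both be true: a screening grade, then a Day 1 baseline grade. The first and third cannot both be followed as written unless Baseline and Day 1 happen to fall on the same day. The empty Day 1 cells do not look like a text-extraction fault, because the same column carries the PK mark and footnote b independently omits Day 1.

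**2. The plan's own design (Section 14.0)**

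Inputs: null rate 0.10, target rate 0.30, first stage of 16 patients stopping at 1 or fewer responses, 25 patients in total, promising if more than 4 respond, both errors set at 0.10. Treating response as one yes/no outcome with probability p at both stages:

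P(promising) = Σ (x = 2 to 16) P[Bin(16, p) = x] × P[Bin(9, p) ≥ 5 − x]

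- p = 0.10: 0.0951, with probability of early stopping 0.9^16 + 16 × 0.1 × 0.9^15 = 0.515
- p = 0.30: 0.9030

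Both errors are within 0.10, and a full search for the minimax design returns the same 16/1 and 25/4. The design figures are not in dispute.

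**3. Illustration of sensitivity (assumption, not a document figure)**

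Let q be the share of otherwise non-responding patients who are counted as responders only because their grade fell between an early Baseline and the first dose. At a 10% rate among the rest, the apparent rate is p = 0.10 + 0.90q.

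| q | Apparent rate p | Extra apparent responders in 25 (25 × 0.90q) | P(promising) |
|---|---|---|---|
| 0 | 0.100 | 0 | 0.095 |
| 2% | 0.118 | 0.45 | 0.160 |
| 5% | 0.145 | 1.1 | 0.285 |
| 10% | 0.190 | 2.25 | 0.519 |

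Five responders are enough for a positive result, so about one extra apparent responder takes the false-positive chance from 0.095 to 0.285.

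**4. Which pre-dose changes could count**

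- A fall from grade 2 to 1, or 3 to 2, counts under the 1-grade definition (Sections 2.0, 4.1 and 12.0). By itself it does not count under the grade 0 success wording in Section 14.0.
- A fall to grade 0 counts under either wording, but only if the patient is dosed although Section 9.1 requires grade 1 or more.

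**The case against.** Section 10.4 is the governing text for the primary endpoint and equates baseline with day 1. Section 8.6 also calls the Day 1 PK sample the baseline. Table 4 is an overview, and its 14-day header also covers laboratory tests and stool studies that have their own 14-day windows (Sections 8.2 and 8.3). The only text that gives a window for a CTCAE screening grade limits it to 7 days. Eligibility requires grade 1 or more on at least 4 of the 7 days before screening and inclusion (Section 6.1), which makes a brief flare less likely to qualify. If Section 9.1 is checked on Day 1, patients who have settled to grade 0 do not start.

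Much of this stands. A reader might infer that three sections contradict one another. The documents do not support that, since a screening grade under Section 8.4 can precede a Day 1 baseline. The 14-day gap is a maximum, and nothing arises at a site that follows Section 10.4. The 4-of-7-days criterion does reduce the risk, but it is tied to screening and inclusion, not to the first dose.

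What the objection does not remove is that Table 4 omits the grade on which Section 10.4 relies, and with it any scheduled means of checking Section 9.1 on Day 1.

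**Conclusion.** The point holds as a conflict between Table 4 and Sections 10.4 and 10.5 over the reference assessment for the primary endpoint and for PRO-CTCAE. The Bristol baseline shares Table 4's timing and has no stated day elsewhere. Where Table 4 is followed and Baseline precedes Day 1, a pre-dose change can be reported as a colesevelam effect.

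A reader might take the 28.5% or 51.9% above as the trial's actual false-positive rate. The documents do not support that, for three reasons:

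- They give no rate of pre-dose improvement, so q is an assumption.
- A pre-dose fall to grade 0 counts only if Section 9.1 is not checked on Day 1, and a partial fall counts only under the 1-grade definition.
- The 10% null is a rate of observed improvement and may already include some spontaneous improvement, in which case the inflation is smaller.

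The textual mismatch is certain; the size of its effect on type I error is unknown. It should be corrected because the endpoint is a change from a value with no single date and the correction is cheap.

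**What to change.** 1. In Table 4, add the stool diary/CTCAE grade, Bristol scale and PRO-CTCAE at Cycle 1 Day 1, before the first dose of colesevelam.
2. In Sections 10.4, 10.5, 12.0 and 14.0 and in footnote b, name that pre-dose Day 1 assessment as the reference for the primary endpoint and for the Bristol and PRO-CTCAE changes. Sections 10.4 and 10.5 already say day 1 for the grade and PRO-CTCAE. What is new is that it precedes the dose and that the Bristol scale is included.
3. Keep the earlier assessment for screening only. Use a different term for the patient's usual bowel pattern, which the response definition also calls baseline.
4. Reconcile Sections 8.0, 8.4, 9.1 and Table 4 on when the grade 1 or higher requirement is assessed. That decision is for the investigators.

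Cost: text edits, existing questionnaires that together take 10 to 20 minutes (Section 10.5), and possibly a brief Day 1 contact for patients outside the PK subset. The sample size and decision rule are unchanged. The change does not remove regression to the mean after Day 1, which a single-arm design cannot separate from a drug effect.

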4.2 Intervention

All patients should be on maintenance single agent lenalidomide and experiencing grade 1 or higher diarrhea according to the CTCAE grading system. For treatment with colesevelam, the starting dose will be 1250 mg (2 x 625 mg) with food which can be increased to 6 tablets max per day based on efficacy and tolerability. Coleveselam should not be taken within 4 hours before or after lenalidomide and other interacting medications. All participants will be given a pill diary to record intake of colesevelam (Appendix 1). The effect of colesevelam on lenalidomide-associated diarrhea will be evaluated after 1, 2, 4, 12 weeks after start of treatment. If the diarrhea does not respond to the starting dose of colesevelam, the dose can be increased every 2 days to 2 tablets two times per day (2 x 625 mg BID) and later to 3 tablets two times per day (3 x 625 mg BID). The colesevelam dose can be decrease to 1 tablet per day if there has been improvement of diarrhea but emergence of side effects. Treatment with colesevelam will continue until drug-related toxicity, diarrhea that remains grade 1 or higher at week 2 despite dose elevations, or if worsening diarrhea occurs, or up to 12 weeks on study.

Patients will be evaluated by their physician and/or research nurse at baseline, after 1 week (+/- 2 days), after 2 weeks (+/- 2 days), after 4 weeks (+/- 7 days), and 12 weeks (+/- 7 days) for efficacy, toxicity, and compliance. The evaluations after 1, 2, and 4 weeks will preferably as office visits but can be replaced by telephone calls for sake of convenience.

Pharmacokinetics will be assessed in a subset of patients (up to 15 patients) at baseline and 8 days after start of colesevelam. All patients will be asked to participate in the PK studies and the first 15 who consent to this correlative part will be included. Research stool samples will be collected for all study participants at baseline and after 12 weeks of study.

Patients that repond to colesevelam can continue on the drug after the 12 weeks of study treatment. Coverage for colesevelam costs after the 12 weeks will not be covered by the trial but will go through patient's insurance.

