Colesevelam hydrochloride, the active pharmaceutical ingredient in Welchol®, is a non-absorbed, lipid-lowering polymer that binds bile acids in the intestine, impeding their reabsorption.

Storage

Store at 25°C (77°F); excursions permitted to 15°C to 30°C (59°F to 86°F). Protect from moisture.

Pharmacokinetics and Drug Metabolism

Colesevelam hydrochloride is a hydrophilic, water-insoluble polymer that is not hydrolyzed by digestive enzymes and is not absorbed. It is not metabolized systemically and does not interfere with systemic drug-metabolizing enzymes such as cytochrome P-450. In 16 healthy volunteers, an average of 0.05% of administered radioactivity from a single ¹⁴C-labeled colesevelam hydrochloride dose was excreted in the urine.

Prescribing Information

Welchol (colesevelam) will be provided free of charge from Daiichi Sankyo, Inc. to the research subjects for 12 weeks durations only.

Administration

Patients should be advised to take Welchol® tablets with a meal and liquid. It can be taken to a maximum of 6 tablets once daily or 3 tablets twice daily.

Interactions

Colesevelam interacts with a number of drugs. Drugs with known interactions with colesevelam (cyclosporine, glimepiride, glipizide, glyburide, levothyroxine, olmesartan medoxomil, oral contraceptives [ethinyl estradiol, norethindrone], and metformin extended release) should be administered at least 4 hours prior to, or after colesevelam. Clinical trials and postmarketing reports in patients treated with colesevelam to reduce serum cholesterol include:

- Increased incidence of hypoglycemia in patients with diabetes mellitus
- Increased seizure activity or decreased phenytoin levels in patients receiving phenytoin. Administer phenytoin 4 hours prior to colesevelam.
- Reduced International Normalized Ratio (INR) in patients receiving warfarin. Monitor INR.
- Elevated thyroid-stimulating hormone (TSH) in patients receiving thyroid hormone replacement therapy. Administer thyroid hormones 4 hours prior to colesevelam.

Drugs that have not been tested for interaction with colesevelam, especially those with a narrow therapeutic index, should also be administered at least 4 hours prior to Welchol. Therefore in the published case-series, the investigators chose to separate lenalidomide administration from colesevelam administration by 4 hours. However, there is no information on potential effects of colesevelam on the absorption and pharmacokinetics of lenalidomide.

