10.5 Symptom and diet assessments (secondary endpoints)

GI symptoms will be assessed at each follow-up (baseline; day 1 of colesevelam), at 1 week (+/- 2 days), 2 weeks (+/- 2 days), 4 weeks (+/- 7 days), and at 12 weeks (+/- 7 days) and will be instructed to fill in the GI oriented PRO-CTCAE questionnaire. The PRO-CTCAE for Gastrointestinal Symptoms is a 10-item multiple choice questionnaire using a 5-point Likert-type response format (Appendix 4). There is no composite score for this instrument. All items in this questionnaire will be analyzed individually.

Diet will be recorded using a questionnaire for dietary intake at set time points during the study (Appendix 5). In the diet questionnaire, patients will record their dietary intake at baseline and at the follow up at week 1, 2, 4, and 12 after starting colesevelam. We will record dietary intake and ask whether the patients have changed their diet as a results of the diarrhea and/or lenalidomide or colsevelam treatment.

Consistency of bowel movements will be graded using the Bristol Stool Form Scale which was developed for patient use.³ Bristol Stool Form Scale categorizes stools into one of seven types based on stool consistency (Appendix 3).

These questionnaires together take between 10 and 20 minutes to complete. These instruments will be given to the patient at the start of the study and will be handed in at clinical visits or can be sent to MSK in the event that visits are replaced by a phone call (see section 4.2).

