the diarrhea responds to colesevelam. The proportion of patients who have had a change in their diet due to diarrhea, and the proportion who had a diet change due to either lenalidomide or colesevelam will be reported

- Patient diarrhea will be further summarized during the study period using the Bristol Stool Form Scale. The scale has seven types of stool consistency. The proportion of patients with improvements in stool consistency from baseline to weeks 1, 2, 4, and 12 will be calculated along with a 95% exact confidence interval.
- The proportion of patients with sustained response by week 12 (end of study) will be calculated with a 95% exact confidence interval. This is calculated as the proportion of patients who have grade 0 diarrhea at week 12 among patients who achieved grade 0 diarrhea by the week 4 assessment.

Correlative studies

Lenalidomide pharmacokinetics while on colesevelam will be described in up to 15 patients treated on this study; the changes from baseline will be reported.

Stool samples will be analyzed for changes in gut microbiota that take place before and after 12 week of colesevelam treatment. Changes in alpha diversity will be summarized using average change in the Inverse Simpson index. Microbial ecology and metagenomic analysis will be performed to describe changes in gut microbiota throughout the study.

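### The week 12 window runs past the 12 weeks of supplied colesevelam, so week 12 outcomes can mix patients who are on and off the drug

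*Combined protocol and SAP*

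**What the plan says.** - **Drug supply.** Section 5.2 provides colesevelam "to the research subjects for 12 weeks durations only". Section 9.1 caps on-study treatment in the same way: "or for a maximum of 12 weeks of treatment".
- **Drug after week 12.** Sections 4.2 and 9.1 let responders carry on, but "Coverage for colesevelam costs after the 12 weeks will not be covered by the trial"; the cost passes to the patient's insurance.
- **Week 12 window in the text.** Section 4.2 evaluates patients at baseline, at weeks 1, 2 and 4, "and 12 weeks (+/- 7 days) for efficacy, toxicity, and compliance". Section 10.5 repeats the tolerance for symptoms, "and at 12 weeks (+/- 7 days", and Sections 10.1, 10.2 and 10.4 use the same 7 days.
- **Week 12 window in Table 4.** The column is headed "12 weeks / End of Cycle 3 (+/- 21 days". It covers the stool diary, Bristol scale, PRO-CTCAE and the research stool sample.
- **Sustained response.** Section 14.0 defines it as "the proportion of patients who have grade 0 diarrhea at week 12 among patients who achieved grade 0 diarrhea by the week 4 assessment". Drug status at week 12 is not part of the definition.
- **Second stool sample.** Sections 8.7 and 10.7 call for it from all patients once 12 weeks of therapy are complete and give no window. Section 14.0 analyses the change from before to after 12 weeks of colesevelam.
- **Drug intake record.** Every patient keeps a pill diary (Section 4.2) and brings it to each clinic visit (Section 10.9). Table 4 makes week 12 an in-person visit.

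**The concern.** Both windows are symmetric around the time when supplied drug ends, so part of each lies after it. At a visit in that part, a patient who obtained colesevelam through insurance is assessed on the drug, and one who did not is assessed off it. The definitions and planned summaries treat the two alike.

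If diarrhea returns once the drug stops, a patient who was well controlled throughout the supplied course could be counted as having lost response on colesevelam. A stool sample taken some days after the last dose could likewise be read as an on-treatment sample in the microbiota and bile acid comparison. Week 12 Bristol and PRO-CTCAE results are exposed in the same way. For sustained response the bias would run against colesevelam, and it could depend partly on insurance coverage.

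**Working it through.** **1. The plan's own calculation.** The only calculated figure is the Simon design in Section 14.0: stop at 1 or fewer of 16, promising at more than 4 of 25, rates of 10% and 30%, both errors 0.10. The probability of declaring the treatment promising is the sum over x = 2 to 16 of P(X1 = x) × P(X2 ≥ 5 − x), with X1 ~ Bin(16, p) and X2 ~ Bin(9, p). It is 0.0951 at p = 0.10 and 0.9030 at p = 0.30, and a full search confirms 25 as the smallest total. The figure reproduces. It rests on response by week 4, so nothing below changes it.

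**2. Windows against supply.** Supply is 12 × 7 = 84 days. Taking week 12 as day 84:

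- Text: 84 − 7 = day 77 to 84 + 7 = day 91. Days after day 84: 7 of 15 (47%).
- Table 4: 84 − 21 = day 63 to 84 + 21 = day 105. Days after day 84: 21 of 43 (49%).

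Choosing one window over the other shortens the overrun but does not remove it.

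**3. Recall period.** Section 12.0 grades the primary endpoint on the average number of stools over the previous two days. If the same recall applies at week 12 (an assumption), a grade rests wholly on days after supply only from day 87, when the recalled days are 85 and 86. That leaves days 87 to 91 (5 days) in the text window and days 87 to 105 (19 days) in Table 4. Most of the exposure therefore comes from Table 4, which is also the only numeric window that covers the stool sample.

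**4. What one patient is worth.** At the 30% target, 0.30 × 25 = 7.5, so about 8 responders, assuming all of them reach grade 0 and enter the sustained response denominator. One patient is then 1/8 = 12.5 points. With two off-drug relapses, for example:

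- 6/8 = 75% (exact 95% CI 35% to 97%)
- 4/8 = 50% (exact 95% CI 16% to 84%)

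At the smallest promising result, 5 of 25, one patient is 1/5 = 20 points.

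**5. Range under assumed rates.** The documents give no rate for coverage, late visits or off-drug relapse. Let f be the fraction of responders assessed off drug. The reported proportion is (1 − f) × on-drug rate + f × off-drug rate. With 80% sustained on drug:

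- Off-drug rate 80% (no loss): 80% at any f.
- Off-drug rate 40%: f = 0.25 gives 0.60 + 0.10 = 70%; f = 0.50 gives 0.40 + 0.20 = 60%.
- Off-drug rate 10%: f = 0.25 gives 0.60 + 0.025 = 62.5%; f = 0.50 gives 0.40 + 0.05 = 45%.

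The effect runs from nothing to 35 points (80% to 45%), depending wholly on inputs that the plan does not supply.

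**The case against.** A reader might infer that the week 12 results necessarily mix the two groups. The documents do not support that. A visit by day 84 has no supply gap, responders may continue without a break, and nothing says that patients will stop, go uncovered or relapse. The plan permits mixing; it does not force it.

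A reader might also infer that the two groups cannot be told apart, or that every late assessment is off drug. Neither follows. The daily pill diary, returned at an in-person visit, should show the last dose during study treatment. What is missing is a rule that uses it. An insured responder seen on day 95 may still be taking colesevelam, so calling that visit off-drug by its date would misclassify the patient and shrink a denominator of about 8.

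Three further points have force:

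- **Day 84 is itself an assumption.** Section 9.2 allows colesevelam to be held with lenalidomide, and the documents do not say whether held days count toward the 12 weeks. Some patients could still have supplied drug after day 84.
- **Seven days is an ordinary scheduling tolerance.** Once Table 4 is brought into line with the text, the remaining exposure is small, though not zero.
- **The window is not the only route off drug.** Holds, and early removal combined with stool sampling from all patients, create off-drug results too. A window edit alone would not reach them, which is a reason to classify by drug status.

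Imprecision with about 8 responders is indeed large. But the exact interval describes sampling error and does not cover a shift caused by assessing patients after the drug has stopped.

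**Conclusion.** The concern holds as a gap between the assessment window and the drug supply. Taking week 12 as day 84, assessments are allowed up to 7 days (text) or 21 days (Table 4) after supplied drug ends, later drug is optional and insurance-dependent, and no week 12 definition or analysis refers to drug status. Sustained response, week 12 Bristol and PRO-CTCAE results, and the second stool sample can therefore combine patients on and off colesevelam.

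The size cannot be estimated from the documents. The 12.5 points per off-drug relapse illustrates sensitivity with about 8 responders and is not a forecast; with no loss of response off drug, the sustained response proportion would not move. It would go too far to conclude that the durability estimate will reflect insurance coverage, since that needs late visits, lapses in coverage and relapse to occur together. Only secondary and correlative outputs are touched: the week 4 primary endpoint, its decision rule and N = 25 stand. The change is worth making because it is cheap and these outputs are the plan's evidence on durability and mechanism.

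**What to change.** 1. Reconcile the week 12 window in Table 4 with Sections 4.2, 10.1, 10.2, 10.4 and 10.5, and state the window for the research stool sample in Sections 8.7 and 10.7.
2. Schedule the week 12 assessment and stool sample on or before the last supplied dose, for example with a window that closes at the end of week 12. State how held days count toward the 12 weeks.
3. Take from the pill diary the date of the last colesevelam dose before the assessment and before the sample. Keep the diary running until both are done, so that doses after week 12 are captured.
4. In Section 14.0, classify each week 12 result by actual drug status, not visit date. Late assessments of patients still taking colesevelam stay in the on-treatment sustained response and stool-change summaries. Off-drug assessments, whatever their cause, are reported separately.
5. Also show sustained response with all responders in the denominator, so that the split does not hide patients.

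This changes assessment timing and analysis only; it leaves dosing, treatment duration, sample size and the primary analysis as they are. The cost is a table and text edit, less flexibility in booking the last visit, and one more descriptive split in a small sample.
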